Subjects that are ineligible for both the allopurinol/placebo and (isocaloric) low fructose arms or do not want to pursue the 6-month intervention will be offered the opportunity to participate in the hypocaloric low fructose arm. Participants that have previously failed initial screening (were ineligible to participate in arm 1 or 2 of the study) will be offered the opportunity to re-consent to the study and have vascular measurements taken at an additional paid screening visit and to enroll in the 5-month long hypocaloric low fructose arm (arm 3).

B. Baseline/Formal Consenting Visit

The subject will arrive to the CRC in the morning to perform further metabolic and vascular tests (**Figure 9**). The subject is instructed to hold their glucose lowering AM medications (subject will resume regular medications after the visit has been completed), and not to eat or drink anything besides water for at least 10 hours before this visit. The subject is also told not to exercise the

[figure not shown]

Figure 9. Order of events at the Baseline Visit occurring at the clinical research center (CRC).

morning of this visit. The visit will take up to 8 hours and the subjects must be fasted. Upon arrival, the participant meets with one of the study's physicians to review and sign the study consent forms. The subject then voids and the study staff takes anthropometric measurements and repeats a DEXA scan at the discretion of the investigator. Subjects will then be placed supine in a quiet, climate-controlled room (22–23 ° C) to rest before vascular measurements are repeated by study staff, including: cIMT, PWV, Glycocheck, FMD and NIRS. Vital signs are measured and an IV line is placed in each arm by the nurse in order to draw blood and infuse during a hyperinsulinemic-euglycemic clamp. The CRC vascular procedures will be repeated again at interim and final visits at 3 and 6 months.

C. Interim visit

An interim visit will include fasting blood draws. Study staff will assess blood pressure, heart rate, weight, and waist circumference as well as body composition (DEXA), cIMT, FMD, NIRS, Glycocheck, and cfPWV. This visit will take up to 4 hours and must occur in the fasting state.

D. Final visit

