A final appointment will repeat all baseline measurements including DEXA, cIMT, Glycocheck, cfPWV, FMD, NIRS and insulin clamp with CEU. The study staff will assess the body weight, waist circumference, heart rate, and blood pressure. Blood will be collected at the beginning and throughout the study procedures at this visit. This visit will take up to 8 hours and must occur in the fasting state. Following the final visit, the treatment portions of each arm are over. Subjects in Part 2 will be offered a meeting with the dietitian nutritionist to discuss diet and exercise. Subjects may be asked to complete an exit survey upon completion of the study. Exit surveys will be administered via Qualtrics or in person depending upon subject preference.

E. Special Consideration in case of unforeseeable hardships such as public health emergencies or weather-related events

In the event that subjects are not able to complete study visits for the reasons described above, the following remedial steps will be taken:

1. Safety visits #4, 6 and 7 at weeks 8, 16, and 20 (respectively) can be completed via a phone interview during which the subject will answer the safety questionnaire (no changes in compensation).
2. In the case that the subject cannot complete safety visit #3 at week 6, every effort will be made to complete this visit within 7 days of the originally scheduled date. In the case that the visit cannot be completed, the subject will be instructed to discontinue the study medication and his/her participation in the study will be completed. [name], who oversees the allopurinol/placebo treatment with the Principle Investigator will be informed.
3. In the case that safety visit #4 at week 8 cannot be completed, and providing the subject has completed at least 2 in-person visits since the medication was started, study medication will be mailed by investigational pharmacy for the subject to continue treatment. [name] will be informed.
4. In the case that the subject cannot complete dietary counseling in person, counseling visits may be completed via phone or comparable, secure tele-counseling set-up.
5. In the case that subjects are unable to complete their interim visits at the originally scheduled date, their visits may be scheduled +/-14 days of the originally scheduled date. If the interim visit cannot be completed onsite, safety formulary will be completed via phone.

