6. In the case that subjects are unable to complete their final visits at the originally scheduled date, their visits may be scheduled +/-14 days of the originally scheduled date provided that the subject maintains the assigned intervention for the duration of the study.
7. In the case that the Clinical Research Center is unavailable or at the discretion of the primary investigator, safety visits may be completed at MUPAW.
8. In the event of the clinical research center not being available or if it is considered by the study physician that performing studies there can increase risk of exposure to infectious agents or related hazards, the following alternative sites will be made available for screening, safety and study visits:
 - Medical school room NW404
 - University hospital clinic rooms

These locations are not carpeted and we do not anticipate an increased risk for the subjects given that medical supervision and nursing staff assistance will be unchanged.

F. Description of Study Procedures

Metabolic testing: As described in the background section, hyperuricemia is characterized by increased inflammation and insulin resistance. We will monitor changes in inflammation and oxidative stress markers through fasting blood sample measurement of serum concentrations of XO activity, TNF α , IL6, CRP, PAI-1, MCP-1, E-selectin, MDA, 3-NT, TBARS, oxidized LDL and 8-iso PGF2 α . In addition, this blood sample will also be used for measurement of fructose, blood lipids, glucose, insulin, creatinine, estradiol, estrone, testosterone and sex-hormone binding globulin, uric acid, blood lipids, and estrogen, the latter used as a covariate.⁷⁰

DEXA scan: to assess body composition with dual-energy X-ray absorptiometry.

Arterial Stiffness and Blood Pressure: The SphygmoCor XCEL device will be used to assess blood pressure and aortic pulse wave velocity, a marker of arterial stiffness. A blood pressure cuff will be wrapped around the upper leg. It will periodically inflate to ~200 mmHg for less than 60 seconds. A pressure sensor (tonometer) will be placed over the skin of the neck region to obtain the pressure wave form in the carotid artery. The total time for this procedure is 15 min.

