Phlebotomy: The total blood withdrawn will not exceed 550 mL in any 8 week period. Hematocrit is measured during screening and before the interim and final visits to check that it is within safe limits (**Table 3** and **Table 4**). All subjects will be advised to refrain from donating blood during public blood drives, during their participation in this project.

These activities are associated with a small risk of phlebitis, bruising and minor pain. Antiseptic technique will be used by nurses who are experts in phlebotomy and catheter placement. If phlebitis occurs, it will be treated conservatively with heat and when appropriate, with antibiotics.

Time point	Volume of whole blood (mls)
Screening	60
Baseline visit	145
SUA concentration	10
SUA concentration	10
SUA concentration	10
Interim visit	35
SUA concentration	10
SUA concentration	10
SUA concentration	10
Final metabolic test	170
Total	470

Table 3. Blood volume taken over the study in the allopurinol/placebo arm

Adherence and serum and urine biochemistries: The SUA response to drug treatment and the pill counts will be used to assess adherence to the drug/placebo arms. Some plasma will be frozen for analysis of potential biomarkers of cardiac and arterial (CA) stiffness. Estimated glomerular filtration rate (GFR) is calculated via the Modification of Diet in Renal Disease Study equation, $GFR = 175 \times \text{standardized serum creatinine} - 1.154 \times \text{age} - 0.203 \times 1.212$ [if black] $\times 0.742$ [if female], where GFR is expressed as mL/min/1.73 m² of BSA and creatinine is expressed in mg/dL⁷¹.

Indirect calorimetry: Fasting energy expenditure and substrate oxidation are measured at the beginning of the metabolic test. Calorimetry carries no risk, however, this test may cause discomfort in those who are fearful of confined spaces or claustrophobic. Before the procedure is performed, subjects are allowed to become familiarized with the hood used to collect expired gas.

Aortic pulse wave velocity (cfPWV): This procedure poses no risks.

Carotid artery intima-media thickness (cIMT): This procedure poses no risks.

Brachial artery and popliteal flow-mediated dilation (FMD) with NIRS: This is a measurement of endothelial function. There are no risks associated with this procedure.

Oral glucose tolerance test (OGTT): At screening, subjects will have an oral glucose tolerance test performed. This might cause blood sugar levels to be elevated following the completion of the test.

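### Under hardship, VII.E item 2 ends participation after a missed week-6 safety visit, and item 6 may deny a delayed 6-month cfPWV to off-treatment subjects

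*Combined protocol and SAP*

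**What the plan says.** Section VII.E of the protocol sets remedial steps for hardship only: "In the event that subjects are not able to complete study visits for the reasons described above", meaning public health emergencies, weather and similar events.

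- **Item 2** begins "In the case that the subject cannot complete safety visit #3 at week 6". Staff first try to hold the visit within 7 days of its date. If that fails, "the subject will be instructed to discontinue the study medication and his/her participation in the study will be completed". This concerns the allopurinol/placebo arm only.
- **Item 1** treats later safety visits differently: "Safety visits #4, 6 and 7 at weeks 8, 16, and 20 (respectively) can be completed via a phone interview". Missing one of these in person does not end participation.
- **Item 5** gives the month-3 interim visit a ±14-day window with no condition about treatment. Its fallback is: "If the interim visit cannot be completed onsite, safety formulary will be completed via phone".
- **Item 6** gives the month-6 final visit the same ±14 days, but only "provided that the subject maintains the assigned intervention for the duration of the study". It covers all arms.

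On the outcome, section VII.B says: "The CRC vascular procedures will be repeated again at interim and final visits at 3 and 6 months". Section VII.F puts the arterial stiffness procedure at 15 minutes, and section VIII.A states: "Aortic pulse wave velocity (cfPWV): This procedure poses no risks".

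**The concern.** Item 2 joins two decisions that need not go together. Whatever the reason for stopping study drug when the week-6 check cannot be done, that reason does not by itself require the trial to stop measuring the subject. A hardship at week 6 may be over by month 3 or month 6, yet the subject has by then left the study.

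Item 6 places its condition on the 6-month measurement and on no other. The condition concerns adherence, which arises after randomisation and may be related to treatment.

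Allopurinol against placebo (40:20, section VII) is the only randomised comparison in the project; the two diet arms have no randomised control. A 6-month cfPWV that is not taken cannot be recovered later. At stake are some precision and, to an unknown degree, the protection against selection that randomisation gives.

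**Working it through.** **1. Does the text cause the loss?**

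| VII.E item | Visit | If it cannot be held as planned | cfPWV |
|---|---|---|---|
| 2 | Safety, week 6 | 7 days' grace, then drug stopped and participation ended | Months 3 and 6 not collected |
| 1 | Safety, weeks 8, 16, 20 | Phone | Later cfPWV unaffected |
| 5 | Interim, month 3 | ±14 days, no treatment condition; else phone safety form | Month 3 may be lost; month 6 unaffected |
| 6 | Final, month 6 | ±14 days, only if intervention maintained | Not stated if the condition fails |

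For item 2 the loss follows from the wording. For item 6 it is an inference, and it needs two things together: a missed original date and an intervention not maintained. An off-treatment subject who attends on the original date can be measured.

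**2. Does another section restore the outcome?** No. Section VIII.D leaves clinic visits after drug discontinuation to the safety officer's discretion and does not mention cfPWV. Section XII.B lists missing data only as a topic for a semi-annual report. No section provides for off-treatment cfPWV, an intention-to-treat set or a rule for missing cfPWV.

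**3. The plan's own figures.** Inputs from section VI: two-sided alpha 0.05, changes of 0.6 and 0.5 m/s, variability 0.4 m/s. Table 2 labels the last a standard error of the change; it is used here as a standard deviation (SD), which is an assumption. With n per group = 2 × [0.4 × (z₀.₉₇₅ + z_power) / Δ]²:

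- Δ = 0.6: 9.34 at 90% power and 6.98 at 80% (stated: 9 and 7).
- Δ = 0.5: 13.45 and 10.05 (stated: 13 and 10).

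Table 2 is reproduced when rounded to the nearest whole number. Its figures are not in dispute.

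**4. Precision.** The documents do not say how many subjects these rules would affect, so the loss is an assumption, taken as proportional in both groups. The standard error of the difference is SD × √(1/n₁ + 1/n₂), so a loss fraction f multiplies the interval width by 1/√(1−f), whatever the SD.

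- f = 5%: 1/√0.95 = 1.03.
- f = 20%: 1/√0.80 = 1.12.

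With SD 0.4, the 95% half-width (1.96 × SE) is:

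- 40:20 measured: 1.96 × 0.4 × √0.0750 = 0.215 m/s.
- 38:19 measured: 1.96 × 0.4 × √0.0789 = 0.220 m/s.
- 32:16 measured: 1.96 × 0.4 × √0.09375 = 0.240 m/s.

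**5. Power for 0.6 m/s** (independent t-test, two-sided 0.05):

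| Loss (assumed) | Overall, SD 0.4 | One sex, SD 0.4 | Overall, SD 0.8 (assumed) | One sex, SD 0.8 (assumed) |
|---|---|---|---|---|
| 0% (40:20; 20:10) | 100% | 96% | 77% | 46% |
| 10% (36:18; 18:9) | 99.9% | 94% | 72% | 42% |
| 20% (32:16; 16:8) | 99.8% | 91% | 67% | 38% |
| 30% (28:14; 14:7) | 99.4% | 87% | 61% | 34% |

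On the plan's own inputs the cost in power is small overall and modest within one sex.

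**The case against.** The strongest reply is that these rules are narrow. They act only in hardship. Item 2 has one trigger, the week-6 visit, with 7 days' grace, and item 7 allows another place for safety visits. Item 8 provides alternative sites for study visits. Section III.A already allows 10% dropout. All of this stands and limits how often the rules act.

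A second reply is that item 2 losses need not bias anything. The trigger is external, and under section VII.K subjects, investigators and clinical research center staff are blind to allocation, so absence may be unrelated to arm or response. This also stands. A reader might infer that item 2 breaks the randomised comparison or turns it into one of adherent completers. The documents do not support that: they define no completer or per-protocol set, and stopping drug for liver enzymes or hypersensitivity falls under section VIII.D, which does not end participation.

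Third, the condition in item 6 may mean only that treatment should continue until the delayed visit, which fits the instruction in section VII.H to take allopurinol on the morning of the final visit. That reading is possible. It still leaves unstated what happens to a subject who has stopped.

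Finally, cfPWV may carry no risk, but attending during an emergency may, and item 8 itself mentions exposure to infectious agents. Interim and final visits also last up to 4 and 8 hours. This is a reason to make the invitation depend on feasibility. It does not justify ruling out measurement months ahead.

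**Conclusion.** The point holds in a limited form. When item 2 is triggered, a randomised drug/placebo subject loses both post-baseline cfPWV measurements, and no other section restores them. Item 6 appears to deny a delayed 6-month cfPWV to off-treatment subjects, but it is better described as an unclear rule than as a stated exclusion.

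The sure harm is lost endpoint data: an interval about 3% to 12% wider if 5% to 20% of subjects are lost, a range that is assumed. Selection on adherence is possible, mainly through item 6. A reader might be tempted to attach a percentage overstatement of the allopurinol effect. That would require assuming how many leave, from which group, and how they would have responded, and the documents give none of these. It would also presuppose that the target is the effect of assignment regardless of adherence, which the protocol does not say. The case for change is that it is cheap and the data cannot be recovered, not that a bias has been shown.

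**What to change.** Leave the drug-stopping rule in item 2 as it stands.

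- **Item 2:** replace the clause that ends participation with a statement that the subject is still invited, when attendance is feasible, to the month-3 and month-6 cfPWV assessments and is analysed in the assigned group.
- **Item 6:** let the ±14-day window apply to cfPWV whether or not the intervention was maintained, and record adherence at that visit.

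The cost is a protocol and consent wording change and a few extra attendances. These can use the visits already scheduled; a shorter cfPWV-only attendance would be a new visit type and would need describing. Some measurements will be taken off drug and will dilute the on-treatment effect. A supportive on-treatment analysis, labelled as such, can show that effect alongside the comparison as assigned.

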Medications for glucose control (insulin, metformin, gliptins, GLP-1 agonists, sulfonylureas, sodium glucose co-transporter inhibitors), antihypertensives, hormone replacement therapy, antidepressants, anticoagulants, or statins, will be considered during recruitment, analyses (e.g., using covariate analysis) and interpretation.

Exclusion criteria for hypocaloric low-fructose diet intervention (part 3):

- 1) Habitual diet containing low amount of sugars < 5% of total energy intake
- 2) Recent CVD event (stroke, heart failure hospitalization, revascularization or acute coronary event in the last 12 months), abnormal thyroid tests or chronic liver disease, stage IV renal disease (GFR <30) and hyperparathyroidism.
- 3) Use of azathioprine
- 4) Active cancer
- 5) Autoimmune diseases
- 6) Excessive alcohol consumption (>14 drinks/week for men, >7 drinks/week for women)
- 7) Current tobacco use
- 8) Bodyweight change $\geq 10\%$ within the last 6 months
- 9) History of gout or uncontrolled hypertension
- 10) Pregnancy or lactation in women (or women not using contraceptives)

Medications for glucose control (insulin, metformin, gliptins, GLP-1 agonists, sulfonylureas, sodium glucose co-transporter inhibitors), antihypertensives, hormone replacement therapy, antidepressants, anticoagulants, or statins, will be considered during recruitment, analyses (e.g., using covariate analysis) and interpretation.

VI. NUMBER OF SUBJECTS

Sample size calculations are based primarily on satisfying the requirements of Aim 2, i.e. to show that XO inhibition and fructose restriction reduce PWV, and that these interventions are more effective in women than in men. Calculations are based on the paired *t*-test for pre- to post-treatment change, and independent *t*-tests for comparisons between treatment arms. In both cases, we assume an alpha of .05 and a two-sided alternative.

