Following screening, eligible male and female subjects will be assigned to one of the three treatment arms. In the medication arm of the study, they will be randomized to either the allopurinol group (n=40; 20 men and 20 women), or the placebo (n=20; 10 men and 10 women) for 6 months, with a final drug/placebo allocation ratio of 2:1 using a permuted block design with random variation of block size. In the isocaloric low-fructose arm of the study, 20 women and 20 men will be recruited to enter a dietary treatment of fructose restriction for 6 months. In the hypocaloric low-fructose arm of the study, 20 women and 20 men will be recruited to enter a dietary treatment of calorie and fructose restriction for 6 months.

A. Screening/Initial Consenting Visit

The first visit to the CRC will take approximately 6 hours and include a written consent to be screened. The subject is instructed to hold their glucose lowering AM medications (subject will resume regular medications after blood has been drawn), and not to eat or drink anything besides water for at least 10 hours before this visit. The subject is also told not to exercise the morning of this visit. After signing the screening consent form, medical information is obtained by the study team, including: DOB, gender, ethnic/racial category, height, body weight (history of body weight gain or

[figure not shown]

Figure 8. Order of events at the Screening Visit occurring at the clinical research center (CRC).

loss), waist circumference, vitals, and a medical history questionnaire. A fasting blood draw is taken to test for biochemistries. Subjects will also undergo a DEXA scan and vascular measurements including carotid intima media thickness (cIMT), carotid femoral pulse wave velocity (cfPWV), Glycocheck, Near-Infrared Spectroscopy (NIRS), Brachial artery FMD, popliteal artery FMD testing, and OGTT with femoral artery blood flow (**Figure 8**).

An introduction to the clinical trial will be done which includes abbreviated descriptions of the various treatment arms and the placebo arm (no treatment). As soon as the blood biochemistry results are available, the subject is contacted, provided with a copy of the results. If eligible for the allopurinol/placebo arm or (isocaloric) low fructose diet intervention arm, study staff discuss with him/her whether they would like to be consented for enrollment in one of the present studies.

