Brachial and popliteal artery flow-mediated dilation (FMD): Arterial measurements will be performed by imaging the brachial and the popliteal artery longitudinally using high-resolution duplex ultrasonography. Arterial vasodilatory responses to hyperemia (i.e., FMD) will be examined by inflating a cuff, distal to brachial and the popliteal artery, up to 250 mmHg for 5 minutes. Before, during and after rapid release of the cuff, brachial and popliteal artery blood flow velocity and diameter will be continuously measured. In addition, during the FMD measurements NIRS probes will be placed on the tibialis anterior muscle and the forearm; the probe will be secured via an elastic tensor bandage which will be loosely wrapped around the site. These probes will stay attached to the participant for the duration of testing.

Carotid artery intima-medial thickness (cIMT): Wall thickness and diameter of the common carotid artery will be measured using high-resolution vascular ultrasound with a 7.5-12.0 MHz linear array transducer and longitudinal 2D mode (Logiq P5; GE Medical Systems, Milwaukee, WI). The left common carotid artery will be measured 2 cm proximal to the bulb and 2 to 3 cm distal to the bifurcation. For this vascular evaluation, we will measure artery diameter and wall thickness for a brief period of time.

OGTT with leg blood flow: After an overnight fast, a catheter will be inserted into an antecubital vein for sampling of venous blood. Blood will be collected every 15-30 minutes over the next 120 minutes after consuming the glucose beverage (75 grams of dextrose). Moreover, before and during the OGTT, we will be using an ultrasound to measure femoral artery blood flow. Throughout the assessment for leg blood flow, a NIRS probe will be placed on the belly of the tibialis anterior muscle in the same conditions previously described. A pneumatic cuff will be placed below the knee. The cuff will be inflated at 20 mmHg above diastolic blood pressure for 60 s to partially occlude blood flow at the time of the NIRS measurement. The total volume of blood drawn per oral glucose tolerance test will be less than 40mL.

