Sources will include the subject's medical history, physical exam, screening laboratory tests (CMP, lipid panel, uric acid, insulin, A1c), dual-energy X-ray absorptiometry (DEXA, total and regional fat mass and fat-free mass), blood tests, aortic PWV, cIMT, brachial and popliteal artery flow-mediated dilation (FMD), OGTT with femoral artery blood flow results, CEU-insulin clamp results, and food intake. Demographic data (plus other related data: emergency contact person, pregnancy status), blood pressure, and anthropometrics will be measured (height, weight, waist circumference). Each subject in parts 1 or 3 (diet interventions) of the study, will donate up to 410 ml of blood (screening through final visit) which will occur over a period of up to 6 months. For Part 2 drug treatment, each subject will donate up to 470mls of whole blood (screening through final visit) which will occur over a period of 6 months.

K. Blinding and subject safety

All of [name] s laboratory staff will be blinded as they perform biochemical assays on serum from the drug/placebo study, the isocaloric fructose-restriction study, or the hypocaloric fructose-restriction study. [name] and the assistant performing vascular measurements will be blinded. For the drug study, safety officer cardiologist [name], rheumatologist [name] and [name] will review screening values to determine subject eligibility. Once the subject is randomized, the subjects themselves, investigators, and all CRC staff working with the subjects will be blinded to treatment group (allopurinol or placebo). During the fructose-restriction studies, the CRC staff and the study dietitian nutritionist will not be blinded because subjects serve as their own control and all subjects will be changing their diets (cannot blind to this treatment). No adverse effects of fructose restriction are anticipated but should subjects exhibit changes in their health status across any system related or unrelated to the dietary treatment, [name] or [name] will be consulted for advice.

VIII. Potential Risks/Adverse Events

A. Potential Risks to Human Subjects

The following are the potential risks:

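### The carotid wall-thickness instruction places one of its two landmarks beyond the end of the vessel it names

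*Combined protocol and SAP*

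**What the plan says.** The cIMT paragraph in section VII.F (Description of Study Procedures) names the vessel first: "Wall thickness and diameter of the common carotid artery will be measured using high-resolution vascular ultrasound". It then gives the site: "The left common carotid artery will be measured 2 cm proximal to the bulb and 2 to 3 cm distal to the bifurcation". It mentions no internal or external carotid segment. It does not say whether one reading or two are taken, which one is the cIMT value, or that the same segment is used each time.

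cIMT is scheduled at four visits in section VII:

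- Screening (VII.A): "vascular measurements including carotid intima media thickness (cIMT", with the other vascular tests.
- Baseline (VII.B): "vascular measurements are repeated by study staff, including: cIMT, PWV, Glycocheck, FMD and NIRS".
- Interim, month 3 (VII.C): "body composition (DEXA), cIMT, FMD, NIRS, Glycocheck, and cfPWV".
- Final, month 6 (VII.D): "A final appointment will repeat all baseline measurements including DEXA, cIMT, Glycocheck, cfPWV".

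The interim descriptions for the two diet arms (VII.G and VII.I) list PWV, FMD and DEXA without cIMT, so the month-3 reading in those arms rests on VII.C.

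On who measures, section VII.K says that "the assistant performing vascular measurements will be blinded", alongside one other team member.

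**The concern.** The instruction defines where a number is read, so it should point to one place on one vessel. It points to two places, and one of them is off the vessel. An operator can keep to the named vessel and ignore the second landmark, read both places and label both common carotid, or read beyond the bifurcation. The text does not exclude the last two.

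The stake is whether cIMT and carotid diameter can be interpreted. A branch is a different vessel, so its wall thickness and diameter are not common-carotid values. With up to four readings per subject over about six months, a change is meaningful only if the segment stays the same. Blinding the vascular staff hides treatment; it does not fix the site.

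**Working it through.** The document states no figure for cIMT, so there is none to reproduce. The check is of the text, with a little arithmetic.

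**1. The landmarks against the vessel.**

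| Element in VII.F | Position | On the common carotid? |
|---|---|---|
| Named vessel | Left common carotid, which ends at the bifurcation | – |
| First landmark | 2 cm proximal to the bulb | Yes |
| Second landmark | 2 to 3 cm distal to the bifurcation | No; only the branches lie there |

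**2. Could they be one site?** Read literally, they lie on opposite sides of the bifurcation. Their separation is at least 2 + 2 = 4 cm to 2 + 3 = 5 cm, plus any length of bulb below the bifurcation, which the document does not give. They are not one site.

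**3. Could a loose reading reconcile them?** Suppose the second landmark was meant as 2 to 3 cm below the bifurcation. The first lies 2 cm plus the bulb length below it. For an assumed bulb length of 0 to 1 cm that is 2 + 0 = 2 cm to 2 + 1 = 3 cm, which matches. One segment described twice is therefore plausible. It is not what the words say: the same sentence uses proximal in its ordinary sense, and the preceding FMD paragraph uses distal in its ordinary sense for cuff placement.

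**4. Does another section settle it?** Sections VII.A to VII.D, VII.H and VIII name the measurement without a site. None corrects the landmark or fixes the segment across visits.

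**5. What would inconsistency do?** Let C(v) be the true common-carotid value at visit v, d the branch-minus-common difference (taken as constant), and s(v) = 1 if the branch was read and 0 otherwise.

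Recorded change = [C(6) − C(0)] + d × [s(6) − s(0)]

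- If the same site is read both times, s(6) = s(0) and the second term is zero. The same holds if the two sites are averaged in the same way at every visit.
- If the site differs, that subject's change is off by d in one direction or the other.
- One such subject moves an arm mean by d/n. With n = 40 (the planned allopurinol arm and each diet arm) that is d/40, or 2.5% of d. With n = 20 (one sex within such an arm) it is d/20, or 5% of d.

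Neither d nor the number of affected subjects is in the document, so the calculation stops there.

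**6. What depends on cIMT?** Section VI says the sample size is primarily for Aim 2, "to show that XO inhibition and fructose restriction reduce PWV". Aim 1 in section I.B assesses stiffness by carotid-femoral PWV. cIMT appears in neither aim, in no hypothesis and in no row of Table 2, and no analysis of it is specified.

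**The case against.** The strongest reply is that this is a slip that a competent sonographer would not act on. The vessel is named in both sentences, the side is given, no branch is mentioned, and the first landmark is usable. An operator who keeps to the named vessel has one place to measure. Section VII.K suggests a small measuring team, although VII.B refers more generally to study staff. Most of this stands: only the second landmark is impossible, and nothing shows that operators imaged different vessels. What does not stand is that the text resolves itself. It leaves the operator to notice the conflict and choose.

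A reader might infer more: that the recorded change in cIMT would be mostly a site difference, several times any treatment effect. The document does not support that, for two reasons.

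- A constant site difference cancels in within-subject change, as shown above. Reading two sites the same way each time alters what is measured; it does not turn the change into a site difference.
- Setting one subject's misreading against a group-mean effect compares unlike things. Purely for illustration, assume d of 0.05 to 0.2 mm and a mean effect of 0.02 mm; neither comes from the document. One misread subject in 40 moves the arm mean by 0.05/40 = 0.00125 mm to 0.2/40 = 0.005 mm, which is 6.25% to 25% of that effect. In a sex subgroup of 20 the share is 12.5% to 50%. Large bias would need frequent inconsistency in one direction, and nothing in the document suggests that.

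**Conclusion.** The point holds as a landmark error in one operative measurement instruction. The second landmark is not on the named vessel, it conflicts with the first, and no other section corrects it. The conclusion rests only on the common carotid ending at its bifurcation, which is basic anatomy.

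The harm is conditional. Following the phrase literally would label a branch reading as common carotid. If the site varied between visits, change in cIMT and carotid diameter would be unreliable. Whether either happened, and by how much results would move, cannot be determined from the document.

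The reach is narrow: one additional vascular measure and the diameter taken with it. It would be wrong to infer that the main comparisons are compromised, since the PWV results, the aims and the sample size do not depend on it. The correction is desirable, not essential.

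**What to change.** In the cIMT paragraph of section VII.F, reconcile the two landmarks into one segment within the left common carotid. The simplest edit is to delete the second landmark and keep 2 cm proximal to the bulb. If the investigators meant one segment described twice, they can restate it in their own terms, provided it lies on the common carotid. Add a sentence requiring the same segment at screening, baseline, interim and final visits.

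For readings already taken, the investigators should confirm and record where they were made. Any taken beyond the bifurcation should be excluded from the common-carotid value. The proximal segment can be re-read only if images were stored; the document does not say that they were.

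The cost is a one-phrase correction, one added sentence and a note to the operators, plus re-reading time only if it proves necessary and possible. It adds no procedure, visit or burden for subjects.
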